## 1. Summary of Research

**Evidence of need:** People who use illicit opioids (PWUO), such as heroin, are over-represented in urgent and emergency admissions. Late presentation with complications from injecting-related infections and injuries is common, yet retention in hospital care is low. This is a serious problem, associated with: reliance on ambulatory care, complex admissions, unplanned hospitalisation, discharge against medical advice (DAMA), readmission, surgical intervention and high NHS costs.

Our research [1-3], engagement with affected groups, and international evidence [4-9] show that poor management of opioid substitution treatment (OST) in hospital emergency, acute admissions and high burden wards is a primary barrier to timely and effective care for PWUO. Experiences of OST delay or omission can cause severe physical and psychological distress and result in treatment interruption or DAMA to obtain illicit drugs. PWUO experiencing opioid withdrawal can be challenging to manage; improving their experience and feelings of safety in the hospital setting is beneficial for both patients and providers.

**Intervention overview:** This research will optimise, test and evaluate the iHOST toolkit to scale nationally. The toolkit will support hospitals to implement and embed evidence-based practice for optimal management of PWUO in collaboration with community drug treatment services.

iHOST comprises: 1) A 'My Meds' card. A prototype card has been developed with PWUO. This provides information for hospital staff to prioritise and expedite medicines reconciliation, including blank fields for OST prescriber and pharmacy contacts. 2) A helpline for patients and providers run by the charity Release. 3) An online training module for staff in hospital Accident and Emergency (A&E), acute admissions, and high burden hospital wards. 4) A 'best practice' hospital policy template. 5) An iHOST 'champion' to support sustainability post intervention.

**Aim:** To optimise OST management in hospital settings to reduce delayed presentation, self-discharge and emergency readmission among PWUO.

**Research question:** Does the iHOST toolkit reduce delays in OST prescription in two hospitals compared to historical local data, and does this lead to reduced DAMA and emergency readmission of PWUO compared to historical local rates and a national comparator cohort?

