## 2. Background and Rationale

The World Health Organization recommends that opioid substitution therapy (OST) be globally available for people who are dependent on illicit opioids (PWUO)[15]. OST is a medication-assisted intervention where patients are prescribed opioids such as methadone to alleviate symptoms of withdrawal, reduce drug use and help provide stability. The effectiveness of OST for opioid dependence has been well documented, with positive health, societal and economic impacts evidenced such as reduced morbidity, mortality and acquisitive crime [16-19]. There are over 260,000 PWUO in England [20], of whom 140,000 receive OST [21]. This is an ageing population, vulnerable to premature death, illness and infectious disease [22, 23], who are over-represented in urgent and emergency admissions [24-27]. Late presentation with injecting-related complications is common and retention in hospital care is low [24, 28-30]. This is a serious problem, associated with: reliance on ambulatory care, complex admissions, DAMA, emergency readmission, surgical intervention and high NHS costs [9, 28, 30-40].

PWUO experience high levels of stigma, which can prevent them from help-seeking and contribute to health inequities [2, 26, 31, 41]. Our recent research with PWUO in the UK [42] has found that fear of drug withdrawal due to delayed OST provision in hospital settings is also a primary barrier to treatment access and completion [2, 3]. Experiences of OST delay or omission can cause severe physical and psychological

distress for inpatients and result in DAMA, also ward absences and disruption to obtain illicit drugs [8, 9, 28, 31, 43, 44]. The focus of this proposal is on improving continuity of OST provision in hospital settings with the aim of improving the patient experience, reducing presentation delay, DAMA and emergency readmission.

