## FORMATIVE RESEARCH

Among 455 PWUO in London, we found that care delay was common and associated with bacterial infection severity and hospitalisation [1-3]. Inpatient hospitalisation for preventable bacterial infection was reported by 30% (137), of whom 40% (55) developed septicaemia and/or endocarditis [3]. A cycle of DAMA and emergency readmission was common. Primary reasons for DAMA were stigma and drug withdrawal due to delayed OST provision [2]. These are modifiable risk factors. Building on these findings, we requested substance dependence policies from all NHS hospital trusts (118 replied) and conducted workshops with PWUO, drug treatment service and hospital staff, to further understand this problem and identify solutions. We found:

- Poor information and care pathways between hospitals and community drug services.
- Inefficiencies in medicines reconciliation leading to delayed or omitted OST dosing.
- Limited knowledge among hospital staff about opioid withdrawal identification and management.
- Inconsistent substance dependency guidelines across hospital trusts: 59 (50%) stated they had no policy.
- A disempowered patient population, who report feeling unsafe in hospitals and lack advocacy support.

This proposal builds on these findings and aims to address the problems we have identified.

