#### Output 1: Quantitative evaluation (lead DL, VH, AM)

- a. Compare detailed outcomes including those not available in HES such as OST prescription rates, time from admission to OST initiation, at Leeds and Staffordshire hospitals before and after iHOST.
- b. Conduct a controlled analysis of changes in two outcomes available across all HES data (DAMA, 28 day emergency readmission) comparing those with HES codes identifying PWUO in Leeds and Staffordshire hospitals with other hospitals across England, using HES.
- c. Assess the acceptability, reach and perceived impacts of staff training activities through self-complete survey data embedded into the training platform (n~150 staff).
- d. Assess, from dedicated drug treatment service records, MY Meds card uptake among service users.
- e. Undertake a cost-effectiveness / cost-consequences analysis of iHOST compared to not providing it.

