## Analysis

### QUANTITATIVE EVALUATION

Our quantitative analysis of outcomes has two elements: (1) a detailed analysis of OST provision and patient outcomes before and after implementation of iHOST, using data extracted from local clinical systems at iHOST hospitals (i.e. an uncontrolled analysis) and covering all quantitative outcomes and (2) a controlled analysis of the two primary outcomes (DAMA and 28-day readmissions), comparing PWUO in the iHOST sites with other hospitals across England, using patient-level HES from NHS Digital. These two elements will both be implemented during the feasibility stage at UCLH and the formal evaluation at Leeds and Staffordshire hospitals. Depending on local data availability, there may be some differences in the definition of locally measured outcomes between iHOST sites.

**1. Detailed before/after analysis based on local data.** This will involve comparison of OST provision and outcomes before and after implementation of iHOST. We will derive patient-level data on each outcome and use regression to test whether there is a difference in the outcomes for patients admitted in the 12 months before the iHOST “go-live” date and those admitted in the 12 months after this date, adjusting for potential patient-level confounders such as the reason for admission. Outcomes will be grouped into: (a) patient outcomes in all those identified as PWUO; b) characteristics of OST prescribing in those receiving OST.

- a. **Patient outcomes in PWUO:** Based on phase 1 feasibility work a range of approaches will be used to identify PWUO in the participating hospitals including: free test records of OST prescriptions in the community, and diagnostic coded for opioid use those with opioid poisoning or injecting-related injuries. Outcomes will include receipt of OST during admission; DAMA; and 28-day emergency readmissions (all binary outcomes). The analysis will then use logistic regression to compare the probability of each outcome for this patient group in the 12 months before vs. the 12 months after the iHOST “go live” date.

Sensitivity analyses will use wash-out periods 3 months either side of the intervention, as there may be changes in practice in the run up to the start date and the intervention may take some time to embed.

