- b. Amongst people prescribed:** People who are prescribed OST in the hospital will be identified using pharmacy records. The time between admission, prescription of OST, receipt of OST and the OST dose will be obtained from clinical records. These outcomes have been selected in discussion with iHOST partners, with delays to OST and low doses cited as problems. The base population will be all patients receiving OST. The modelling strategy will depend on the distribution of the outcomes, for example analysis of the time between admission and receipt of OST may use gamma regression.

UCLH has investigated the feasibility of collecting these data. The outcomes can be extracted from pharmacy and discharge summary records. We have identified several approaches to defining the patient group discussed in (b), including searching free-text using CogStack software, and will refine these and potentially conduct sensitivity analysis with different patient groups.

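### Time to OST is compared only among patients who received OST, a group iHOST is meant to change, so a real cut in delay can be understated, hidden or in some scenarios reversed

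*Protocol*

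**What the plan says.** The first limb of the research question (Protocol, sections 1 and 4) is: "Does the iHOST toolkit reduce delays in OST prescription in two hospitals compared to historical local data". Time between admission, prescription and receipt of OST is secondary outcome 4, and OST dose is secondary outcome 5.

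Under Analysis, Quantitative evaluation, item 1, the local before/after analysis has two parts.

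- Part (a) covers everyone identified as a person who uses illicit opioids (PWUO): "Outcomes will include receipt of OST during admission; DAMA; and 28-day emergency readmissions (all binary outcomes").
- Part (b) covers time and dose: "People who are prescribed OST in the hospital will be identified using pharmacy records", and then "The base population will be all patients receiving OST".

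Phase 3, Output 1(a) lists both kinds of measure together, "such as OST prescription rates, time from admission to OST initiation", for comparison before and after iHOST.

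On the problem being addressed, the Formative research section names "Inefficiencies in medicines reconciliation leading to delayed or omitted OST dosing". Section 2 says: "Experiences of OST delay or omission can cause severe physical and psychological" distress and lead to discharge against medical advice (DAMA). The helpline component aims to have inpatients either continued on community OST or assessed and titrated in hospital.

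**The concern.** Membership of the delay analysis is settled after admission, and the intervention is designed to affect it. A patient who leaves before a first dose has had the worst possible delay but contributes no waiting time. If iHOST works as the protocol's logic model expects, fewer such patients are lost after go-live than before. The later recipient group would then include people who earlier would have left undosed, and their waits may be longer than average.

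Part (b) also moves between people prescribed OST and people receiving it. Under the stated base population, someone prescribed OST who leaves before the dose also disappears from the prescription-to-receipt interval.

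The national HES analysis cannot help, because the protocol notes that HES does not record OST in hospital. This uncontrolled local comparison is therefore the only quantitative test of delay. Its result is also carried into the cost-consequences table.

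**Working it through.** The protocol gives no receipt rate, mean wait or power figure for time to OST, so there is no stated figure to reproduce. All inputs below are assumptions chosen to show the range.

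**1. Mixture arithmetic.** Let r0 and r1 be the shares receiving OST before and after, m0 the recipients' mean before, m1 the mean after in those who would have received OST anyway, and mn the mean in added recipients.

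Recipients' mean after = [r0·m1 + (r1 − r0)·mn] / r1.

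The apparent change is zero when mn = (r1·m0 − r0·m1) / (r1 − r0).

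- Of 100 patients, 60 are dosed at a mean of 12 h before. After, the same 60 are dosed at 10 h and 20 more at 30 h: (60×10 + 20×30)/80 = 15 h. The recipients' mean rises by 3 h although nobody waits longer.
- Receipt 50% to 60%, existing waits cut 20% (12 to 9.6 h), added recipients at 36 h: (0.5×9.6 + 0.1×36)/0.6 = 14.0 h against 12.0 h. Break-even: (0.6×12 − 0.5×9.6)/0.1 = 24 h.
- Receipt 50% to 70%, 10% cut: break-even (0.7×12 − 0.5×10.8)/0.2 = 15 h.
- Receipt 40% to 45%, 30% cut: break-even (0.45×12 − 0.4×8.4)/0.05 = 40.8 h.

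Reversal is easy when receipt rises a lot and the cut is small, and hard in the opposite case.

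**2. Competing exponentials.** Latent mean time to OST goes from 24 to 12 h; mean time to leaving is 24 h in both periods. The recipients' mean is 1/(1/24 + 1/24) = 12 h before and 1/(1/12 + 1/24) = 8 h after. A true ratio of 0.50 appears as 8/12 = 0.67. The direction is right and the size understated.

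**3. Skewed waits.** Latent time to OST T is lognormal (median 24 h, log-SD 1.2). Time to leaving is exponential with mean d = 72 h. OST counts as received only if it comes first. Then share receiving = E[exp(−T/d)], recipients' mean = E[T·exp(−T/d)]/E[exp(−T/d)], and share given OST by 24 h = E[1(T ≤ 24)·exp(−T/d)]. By numerical integration:

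| OST speed | Time to leaving | Receive OST | Recipients' mean | OST by 24 h, all PWUO |
|---|---|---|---|---|
| before | before | 64.3% | 23.8 h | 42.9% |
| 10% faster | unchanged | 66.5% | 22.3 h | 46.1% |
| 10% faster | ×1.5 | 74.3% | 25.6 h | 48.4% |
| 20% faster | ×1.5 | 76.3% | 23.6 h | 52.1% |
| 30% faster | ×1.5 | 78.4% | 21.5 h | 56.2% |
| unchanged | ×1.5 | 72.4% | 27.5 h | 45.1% |

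Against the before mean of 23.8 h, the five later rows show −6%, +8%, −1%, −10% and +16%, for true changes in speed of −10%, −10%, −20%, −30% and none. The all-PWUO share moves in the right direction in each row with faster OST.

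**4. Milder non-receipt.** Same model, with d set so that 10%, 20% or 30% go undosed before, and reset so that this share falls by one third after. Change in recipients' mean:

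| Undosed before | OST 10% faster | 20% faster | 30% faster |
|---|---|---|---|
| 10% | −3% | −14% | −25% |
| 20% | +2% | −9% | −20% |
| 30% | +8% | −4% | −16% |

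Attenuation is the rule here. Reversal appears only with a small gain in speed and at least 20% undosed.

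**The case against.** The strongest reply is that omission is already analysed. Receipt is tested in all identified PWUO, and prescription rates are compared before and after, so together with time among recipients this is a two-part analysis: whether dosed, then how fast. A reader would see receipt rise beside the mean wait. That stands as real mitigation. But the delay estimate remains conditional on receipt, and nothing says the two results will be read together. Adjustment for reason for admission and the three-month wash-out do not bring back undosed patients. The possible sensitivity analysis with different patient groups concerns how patients are identified.

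Three stronger readings are tempting and are not supported:

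- A reader might infer that the comparison is certainly biased, or that reversal is to be expected. The documents give no receipt rates. Section 2 cites 25–30% of PWUO leaving before completing treatment, dosed or not. The 40% and 50% undosed in steps 1 and 2, and the 36% in step 3, lie above that, although ordinary discharge before dosing could add to it. If receipt and early leaving barely change, the bias is small.
- A reader might extend the point equally to dose. Dose exists only in recipients, so that restriction is natural; what remains is a possible shift in case mix.
- A reader might add that doses given in A&E before admission would have zero or negative times and break the model. The protocol does not define the admission timestamp or say that OST precedes it, and gamma regression is offered only as an example.

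**Conclusion.** The point holds for delay. The protocol fixes the population for time to OST by a post-admission event that it expects iHOST to change, and no planned analysis restores the patients who leave undosed. The before/after comparison can therefore understate a true reduction in delay, hide it, or in some scenarios reverse it. On the assumed inputs, a 10% gain in speed appears as anything from −6% to +8%, and a 20% gain can vanish. Actual size and direction depend on receipt and leaving rates that the documents do not give.

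This is a should-fix. Time to OST is a secondary outcome and the DAMA and readmission analyses are untouched. It still matters, because delay is the first limb of the research question and the presumed route to the primary outcomes.

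**What to change.** - Make the main delay analysis the cumulative incidence of first OST, with DAMA, other discharge or death before OST as competing events. A simpler equivalent is the share given OST within a pre-set time, counting non-receipt as failure.
- Run it in all admissions of identified PWUO, with the main denominator fixed independently of in-hospital receipt. A recorded community OST prescription would serve and is already one of the identification sources in part (a). Use the wider PWUO group as a sensitivity analysis.
- Keep recipients-only time as a supporting result, to be read together with the receipt result.
- Leave dose in recipients, with a note that case mix may shift between periods.

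The cost is small: the pharmacy and discharge records already planned for extraction, plus analysis wording. There are three downsides to state. Some included patients may not have needed OST in hospital. iHOST may itself change who is recorded as PWUO or as having a community prescription. Cumulative incidence also rises when patients simply stay longer (42.9% to 45.1% by 24 h in the last row of step 3), so it measures timely receipt overall and not prescribing speed alone.

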## 4. Aims and objectives

**Aim:** To optimise OST management in hospital settings nationally to reduce delayed presentation, DAMA and emergency readmission among PWUO.

**Research Question:** Does the iHOST toolkit reduce delays in OST prescription in two hospitals compared to historical local data, and does this lead to reduced DAMA and emergency readmission of PWUO compared to historical local rates and a national comparator cohort?

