## Setting/context

**Phases 1 & 2 (Optimisation, Feasibility):** University College London Hospital (UCLH); University College London Hospitals NHS Trust; drug treatment services in the area served by UCLH (NHS Camden and Islington; HumanKind; CGL; Turning Point; Westminster Drugs Project) and GP shared-care services with a high proportion of PWUO clients (such as CHIP, Camden).

**Phase 3 (Evaluation):** St James's University Hospital, Leeds Teaching Hospital NHS Trust; Royal Stoke University Hospital, University Hospitals of North Midlands NHS Trust; linked drug treatment services (operated by Humankind: Staffordshire Treatment and Recovery Service (STARS), Forward Leeds).

**Phase 4 (Dissemination):** we will work with all the sites above (London, Staffordshire, Leeds) to disseminate findings and co-produce outputs.

These sites have been purposefully selected to represent different geographical contexts and high proportion of PWUO A&E and inpatient admissions. A brief overview of the sites involved:

**LONDON:** is home to a large street homeless population and is the only UK city with a statistically significant increase in the number of young opioid users (15 - 24 years). UCLH primarily services the urban boroughs Camden, Islington, Haringey and part of Westminster. For 2019/2020 the number of adults on treatment for opioid use in these boroughs was 980, 880, 745 and 515, respectively (total 3120). UCLH report that 208 inpatient admissions between 1 April 2019 and 31 March 2020 included a methadone prescription. The majority were in infectious diseases, emergency or acute admissions wards. Including those treated for complications of opioid use (such as injecting-related skin abscesses), and those where illicit opioid use is recorded in structured data, this number rises to 500 unique patients per year. A small (1.5 WTE) UCLH Alcohol and Drug Liaison Service cover all wards and departments, including partnership working with community services for onward referrals.

**STAFFORDSHIRE:** is a largely rural area which is relatively affluent but with a few notable pockets of high deprivation. Based on the 2015 Index of Multiple Deprivation, 49 of Staffordshire's 528 lower super output areas fall within the top 20% most deprived nationally. For 2019/2020 the number of adults on treatment for opiate use in Staffordshire was 1685 (NDTMS). The Royal Stoke University Hospital is a general hospital

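### OST delay is analysed only in patients who received OST, a group whose membership iHOST is meant to change, so the before/after comparison of delay is selected on a post-intervention variable

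*Protocol*

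**What the plan says.** Section 4 of the protocol opens its research question with delay: "Does the iHOST toolkit reduce delays in OST prescription in two hospitals compared to historical local data". Outcome Measures lists the times from admission to prescription and receipt of OST as secondary.

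Under Quantitative Evaluation, item 1 compares patients admitted in the 12 months before and the 12 months after go-live. It forms two outcome groups:

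- **Item 1a** covers all identified PWUO. Its binary outcomes, analysed by logistic regression, include whether OST was received during the admission.
- **Item 1b** covers "characteristics of OST prescribing in those receiving OST". It fixes the denominator: "The base population will be all patients receiving OST". The model is left open, but the one example is that "analysis of the time between admission and receipt of OST may use gamma regression". Censoring and competing events are not mentioned. The item's heading refers to people prescribed OST, while the base is people receiving it.

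The Formative Research section names the problem to be solved as "Inefficiencies in medicines reconciliation leading to delayed or omitted OST dosing". The Intervention section expects fewer self-discharges. The training and helpline sections also cover starting and titrating OST in hospital. Item 2 states that HES does not record OST, so no controlled analysis of delay is available.

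**The concern.** Being in the item 1b analysis depends on having received OST, and receipt is something iHOST is designed to change. Two routes follow.

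- **Composition.** Patients who would have gone without OST before go-live may be given it afterwards. If they are slower than those always treated, they raise the recipients' mean even when nobody waits longer.
- **Truncation.** A patient who leaves before a dose has no completed time and drops out. If iHOST keeps such patients in hospital, their long times enter the after period only.

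Both routes push the delay result against iHOST, and more strongly the more iHOST widens provision and reduces early leaving. Adjustment for reason for admission does not remove selection on receipt. The risk is that a real gain in speed is reported as smaller than it is, as nil, or as a loss, on the step of the logic model that is meant to explain any effect on the primary outcomes.

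**Working it through.** The protocol states no figure for OST delay, so there is none to reproduce. Its sample-size statement concerns self-discharge. All delay and leaving values below are assumptions.

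**1. Composition, two groups.** Let p be the share treated in both periods, with mean delay a0 before and a1 after. Let q be the share newly treated after go-live, with mean delay b. The recipients' mean goes from a0 to (p·a1 + q·b)/(p + q). It rises when q(b − a0) > p(a0 − a1).

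Take p = 70%, a0 = 12 h, a1 = 10 h, b = 36 h:

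- q = 5%: (7.0 + 1.8)/0.75 = 11.73 h. The 2-hour gain appears as 0.27 h.
- q = 10%: (7.0 + 3.6)/0.80 = 13.25 h. The gain appears as a loss of 1.25 h.
- Break-even: q × 24 = 0.70 × 2, so q = 5.8%.

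Over q = 5, 10, 20, 30%, a1 = 6, 9, 10 h and b = 24, 36, 48 h, the mean rises in 21 of 36 settings.

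**2. Composition, with counts.** Assume 500 PWUO. Before: 180 patients continuing a prescription (mean 12 h) and 20 new starts (mean 36 h). After: both types 17% faster (10 h and 30 h), with a varying number of new starts.

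- Before: (180×12 + 20×36)/200 = 14.4 h.
- 20 extra new starts: (1,800 + 40×30)/220 = 13.6 h, 5.3% shorter.
- 40 extra: (1,800 + 60×30)/240 = 15.0 h, 4.2% longer.
- 100 extra: (1,800 + 120×30)/300 = 18.0 h, 25% longer.
- Break-even total N: 1,800 + 30N = 14.4(180 + N), so N = 792/15.6 = 50.8, about 31 extra.

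With exponential times and 100 extra, the share of all 500 given OST by 24 h rises from 33.1% to 46.0%, the correct direction.

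**3. Truncation.** Assume exponential times, OST rate λ = 1/24 per hour, and a share s leaving before OST. The leaving hazard is then μ = λs/(1 − s), and the recipients' mean is 1/(λ + μ). Multiply μ by 0.67 after go-live.

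| s | OST speed unchanged | OST mean 24 h to 20 h |
|---|---|---|
| 10% | +3.4% | −12.8% |
| 15% | +5.2% | −10.8% |
| 20% | +7.1% | −8.6% |
| 25% | +9.0% | −6.3% |

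In this model a 17% speed-up is understated but keeps its sign.

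**4. Simulation.** Time to OST is lognormal (median 18 h, sigma 0.8 or 1.2). Time to leaving is lognormal (median 12, 24 or 48 h, sigma 1). OST is received if it comes first. After go-live, OST time is multiplied by 0.8 or 0.9 and leaving time by 1, 1.5 or 2. Each of the 36 settings used 1,000,000 patients.

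- Leaving unchanged: the recipients' mean rose in 0 of 12 settings.
- Leaving delayed: it rose in 17 of 24.
- Attenuation without reversal (sigma 0.8, leaving median 24 h, OST ×0.8, leaving ×1.5): 16.50 to 15.22 h, a fall of 7.8% where every patient's OST time fell by 20%.
- Reversal (sigma 1.2, leaving median 24 h, OST ×0.9, leaving ×1.5): 14.87 to 16.31 h among recipients, while the share of all patients dosed by 24 h rose from 47.5% to 55.7%.
- The share of all patients dosed by 24 h rose in all 36 settings.

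**The case against.** The strongest reply is that the plan describes OST in two parts: who gets it (item 1a, all PWUO) and how fast among those who do (item 1b). In the count example with 100 extra new starts, the receipt outcome would rise from 200/500 = 40% to 300/500 = 60% and be reported beside the delay result. A reader might infer that omitted OST disappears from the evaluation; it does not. What remains is that the receipt outcome does not repair the delay estimate. Having no time limit, it can also rise simply because stays lengthen.

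It is also fair that the premise of slow new recipients has no source in the protocol. Omission is attributed there to medicines reconciliation, and the My Meds card is for people already on OST, so newly treated patients may be quick. Doubling new starts in the count example does not reverse the result. That limits any claim about sign.

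The outcome is secondary, the model is open, and the protocol allows plans to be refined and other patient groups to be tried. The last is tentative and concerns how patients are identified, not the inclusion of undosed patients. The base population is stated without qualification.

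The alternative denominator is not free of selection either. The 1a cohort is found partly from recorded community prescriptions, which the card may make more visible, and includes patients who may not need OST.

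**Conclusion.** The point holds as a should-fix. The delay comparison conditions on receipt of OST, which iHOST is meant to change, so the two periods are selected differently. The result can understate a real reduction in delay. Under some assumptions, namely many slow newly treated patients or substantially later leaving, it can reverse it. The primary outcomes and the HES analysis are unaffected.

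Three stronger readings are not supported:

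- **That the analysis will show harm.** Reversal depends on assumed values. It did not occur when leaving was unchanged in the simulation, nor in the exponential truncation model with a 17% speed-up.
- **That over half the cohort is left out.** A reader might divide UCLH's 208 by its 500 (0.42). The 208 are admissions ("UCLH report that 208 inpatient admissions between 1 April 2019 and 31 March 2020 included a methadone prescription"), while the 500 are unique patients and include people treated for complications of opioid use. UCLH is also the feasibility site. The ratio is not a usable share.
- **That patients prescribed but never dosed are definitely lost from time to prescription.** The heading and the base of item 1b disagree, so their place is unclear rather than fixed.

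**What to change.** In Quantitative Evaluation, item 1:

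- Make the main delay analysis the cumulative incidence of first OST prescription and of first OST dose in all admissions of the 1a PWUO cohort, with self-discharge, other discharge and death before OST as competing events.
- Summarise it as the proportion given OST by an analysis time point fixed in advance. The 24 h used above is only an illustration.
- Repeat it in patients with a recorded community OST prescription, because not all of the 1a cohort need OST and iHOST may change who is identified.
- Keep the recipients-only time model, labelled descriptive.
- Reconcile the heading of item 1b with its base population.

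The cost is a change of wording and model. The cohort, OST times and self-discharge status are already planned extractions; the time of leaving or death must be included with them. The effect is then stated as a proportion rather than mean hours.
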